Cover page

Official Project Title: Reducing Pesticide Exposures in Child Care Centers

NCT # 03319927

Document: Study Protocol

Document Date: 8/13/2025

Study Protocol

UCSF IRB Study Application Section 8.0

8.2 HYPOTHESIS: Describe the hypothesis or what the study hopes to prove (Help Text updated 9/13):

1. Child care center staff who attend the IPM workshop will have significantly increased knowledge of IPM and hazards of pesticide use compared to their pre-workshop knowledge and compared to the control center staff.
- 2.: Post-intervention, the IPM intervention child care centers will have (a) higher numbers of written IPM policies, (b) more IPM practices, (c) fewer pest problems, and (d) higher director self-efficacy for pest management compared to pre-intervention and compared to the control centers.
3. Post-intervention, the IPM intervention child care centers will have lower concentrations and loadings of pesticides in dust compared to pre-intervention and compared to the control centers.
4. Post-intervention, children's personal exposure to pesticides, as measured by silicone wristbands, will be lower compared to pre-intervention and compared to that of children in the control centers.

8.3 AIMS: List the specific aims:

1. To determine if a nurse-led IPM workshop improves child care center staff's IPM knowledge.
2. To determine if an IPM intervention in child care centers (a) increases the number of IPM policies, (b) increases IPM practices, (c) decreases pest problems (i.e., number of pests present, pest debris), and (d) increases director's self-efficacy.

3. To determine if an IPM intervention reduces pesticide contamination in the intervention child care centers compared to the control centers.
4. To determine if an IPM intervention reduces children's and teachers' exposure to pesticides in the intervention child care centers compared to the children in the control centers.

8.4 DESIGN: Briefly describe the study design (e.g., observational, interventional, randomized, placebo-controlled, blinded, cross-over, cross-sectional, longitudinal, pharmacokinetic, etc.):

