A randomized control study will be conducted and include 90 child care centers in four CA counties enrolled in five 9-month cycles over five years. The counties will be matched on rates of poverty, number of children under age five, and annual pesticide usage. The matched counties will be randomly assigned to an IPM intervention or an active control intervention (i.e. physical activity). During the 7-month Intervention phase, trained child care health consultants will host one workshop per center on the intervention topic (IPM or physical activity) and conduct seven monthly consultations per center starting with the center director and the child care health consultant setting center-specific goals.

The 'Follow-Up Study' will assess IPM practices, pests, and pesticides in all of the enrolled child care centers. The directors will complete surveys, the research staff will conduct observations, and a researcher will collect dust samples in the child care centers the same season and month as the baseline period.

BACKGROUND AND SIGNIFICANCE: Briefly provide the background and significance of this study (e.g. why is this study needed) (space limit: one page):

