Post-Intervention Phase. During this phase, a research assistant will re-assess the center using the same observational checklists described for the Baseline Assessment, and the CCHC will also repeat all other aspects of Baseline Assessment data collection, including a director interview, the self-efficacy survey, dust collection, silicone wristband collection (children and teachers) and its attendant data collection from families, and anthropometric measurements. At Post-Intervention, however, no new children will be enrolled to participate. The same families who participated at Baseline will be invited to participate again, provided their child still attends the center and intends to be present on the sampling days.

Follow-up Study. We will also conduct a one-year follow-up study on pesticide exposure for all of the intervention centers, including both dust analyses and assessment of pests and pesticide products .

Sampling Procedures. The silicone wristbands will be sent de-identified to [name] laboratory at Oregon State University and the child care center's dust samples will be sent to Southwest Research Institute (SwRI) located in San Antonio, TX for analysis of multiple pesticides. They will be analyzed within a year of data collection and we will store the amount of

wristband or dust that is left over for 5 years to use in possible future analyses of other environmental chemicals or health markers.

8.11 INSTRUMENTS: List all questionnaires, surveys, interview, or focus group guides that will be used for this study:

If the instruments are not complete or not available because they will be developed as part of this study, describe the basic content or include an outline and submit the final versions to the IRB with a modification for approval prior to use.

1. IPM and Physical Activity (PA) Knowledge Survey – pre and post-workshop
2. IPM and PA Policy Checklist
3. Director interview
4. IPM Checklist ([name] et al., 2012)
5. Director IPM Interview
6. Director and child care provider Self-Efficacy ([name] et al., 2003) – modified Bandura
7. Demographic Survey for child care providers - sex, age, ethnicity,
8. Demographic Survey for parents - sex, age, ethnicity, BMI, health
9. CHAMACOS parent interview -modified as self-completed survey with major life events, physical activity
10. Child Anthropometrics
11. Dust samples ([name] et al., 2012)
12. Child activity measure modified OSRAP (A [name] et al., 2014)

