Cover page

Official Project Title: Reducing Pesticide Exposures in Child Care Centers

NCT # 03319927

Document: **Statistical Analysis**

Plan Document Date 8/13/2025

Statistical Analysis Plan

Frequency tables for all the variables and measures of central tendency and variability for continuous variables were stratified by randomization group to check for imbalances. If the two groups differ significantly at baseline on covariates, we will use methods based on the Rubin causal model (e.g., propensity scores, double-robust estimation) to obtain the desired population-level estimates under the counterfactual assumption of balanced groups. (Luellen, Shadish, & Clark, 2005; Rubin, 2004; Seaman & Copas, 2009; Shadish, Luellen, & Clark, 2006; Weitzen, Lapane, Toledano, Hume, & Mor, 2004) Descriptive analyses will also yield important information about the child care centers' levels of pesticide contamination and child exposures; these data were summarized by group, time, and cohort. Primary inferential analyses were performed using tobit regression models which provided an approach for modeling repeatedly measured and clustered dependent variables in this study. (Verbeke & Molenberghs, 2000) SAS (SAS Institute, 2002). Survey and observational data were analyzed using parametric or non-parametric statistics based on the distribution of the dependent variable aggregated by child care center (n=85). All tests used a priori $p < .05$ as level of statistical significance.

Specific Aim 1. To determine if a nurse-led IPM workshop improves child care center staff's IPM knowledge (a) **Unit of Analysis:** Child care staff aggregated by center. (b) **Dependent Variable:** IPM knowledge score. (d) **Independent Variables: Group and Time.** Paired ttests were conducted to assess change in knowledge at baseline and post-IPM workshop.

Specific Aim 2. To determine if an IPM intervention in child care centers (a) increases the number of IPM policies, (b) increases IPM practices, (c) decreases pest problems (i.e., number of pests present, pest debris), and (d) increases center director's self-efficacy. (a) **Unit of Analysis:** Child care centers. (b) **Dependent Variable:** IPM policy, IPM practices, pest problems, director self-efficacy. (c) **Independent Variables: Group and Time.** Normally distributed dependent variables were analyzed using ttests or ANOVA and non-normally distributed dependent variables were analyzed using Kruskal-Wallis tests.

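### SAP Aim 2 names no paired test for the pre-post half of Hypothesis 2 when an outcome is non-normal, and does not say which contrast Kruskal-Wallis addresses

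*SAP*

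**What the plan says.** Protocol 8.2, Hypothesis 2, sets two comparisons for each outcome. Its last item reads "higher director self-efficacy for pest management compared to pre-intervention and compared to the control centers", and the closing words govern the policy, practice and pest items as well. The pre-post comparison is made within the same centers: under Post-Intervention Phase in Protocol 8.9, "a research assistant will re-assess the center using the same observational checklists described for the Baseline Assessment", and the director interview and self-efficacy survey are repeated too.

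SAP Specific Aim 2 takes the center as the unit, lists the outcomes as "IPM policy, IPM practices, pest problems, director self-efficacy", and gives Group and Time as independent variables. It then chooses the test by distribution alone: "Normally distributed dependent variables were analyzed using ttests or ANOVA", and "non-normally distributed dependent variables were analyzed using Kruskal-Wallis tests". It mentions no pairing, change score, repeated-measures form or center effect.

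The other aims do address the dependence. For Aim 1, "Paired ttests were conducted to assess change in knowledge at baseline and post-IPM workshop". Aims 3 and 4 add a random intercept for center so that the two timepoints of a center may be correlated.

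**The concern.** Kruskal-Wallis refers its statistic to what would be seen if all observations were independent. Applied to Time, it treats the baseline and post values of one center as if they came from two different centers. Any stable difference between centers (building, kitchen, director) then stays in the noise, whereas a paired test removes it. With positive correlation the p-value is too large, and a real fall in pests or rise in policies may be reported as non-significant. Policy and pest counts are natural candidates for the non-normal route.

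If Kruskal-Wallis was used only between arms, the pairing problem does not arise, but the plan then names no test of change from pre-intervention for those outcomes. On either reading, part of a stated hypothesis lacks a suitable named test.

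**Working it through.** The documents give no power, effect size, SD or within-center correlation for Aim 2, so there is no planned figure to reproduce. The check is a range under stated assumptions.

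**Inputs**
- Centers: the SAP's opening paragraph gives n=85 without a split by arm. Assumed 85/2 = 42.5, taken as n = 42.
- Significance level: 0.05 (SAP). Sidedness is not stated; two-sided assumed.
- Pre-post correlation r: assumed 0 to 0.7.
- True shift d: assumed 0.4 SD, with equal SDs at both visits.

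**Step 1: size of the error if pairing is ignored (normal approximation)**

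Unpaired SE = s√(2/n); correct SE = s√(2(1−r)/n). The ratio is 1/√(1−r): 1.00, 1.20, 1.41 and 1.83 at r = 0, 0.3, 0.5 and 0.7.

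Real type I error = 2[1 − Φ(1.96/√(1−r))]: 0.050, 0.019, 0.006 and 0.0003 at the same values.

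Power at r = 0.5, n = 42, d = 0.4:
- Unpaired: Φ[(0.4 − 1.96 × 0.218)/0.154] = 0.43
- Paired: Φ[0.4/0.154 − 1.96] = 0.74

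**Step 2: simulation of the rank tests**

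5,000 replicates per setting, n = 42 pairs, Kruskal-Wallis (KW) against Wilcoxon signed-rank (SR) on the raw difference. For lognormal data, r and the shift are on the log scale.

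| r | KW rejections with no change: normal / lognormal | Normal power: KW vs SR | Loss (points) | Lognormal power: KW vs SR | Loss (points) |
|---|---|---|---|---|---|
| 0 | 4.8% / 4.8% | 41% vs 41% | 0 | 42% vs 38% | −4 (a gain) |
| 0.3 | 1.8% / 2.0% | 40% vs 54% | 14 | 42% vs 51% | 9 |
| 0.5 | 0.6% / 0.8% | 39% vs 69% | 29 | 39% vs 63% | 23 |
| 0.7 | 0.04% / 0.1% | 38% vs 89% | 51 | 37% vs 83% | 45 |

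SR rejects 4.2% to 5.1% of the time with no change. The Monte Carlo SE of a power near 40% is √(0.4 × 0.6/5000) = 0.7 points, and repeat runs agree to about one point (8 and 22 for the lognormal 9 and 23).

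**Step 3: how far the loss depends on the setting**

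With all 85 centers pooled and d = 0.5, the normal approximation at r = 0.5 gives 0.967 unpaired against 0.996 paired, a loss of about 3 points. The loss is therefore not large everywhere.

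**Step 4: other uses of Kruskal-Wallis that the SAP wording allows**
- Post values compared between arms: pairing plays no part, and pre-post is not tested.
- Change scores compared between arms (42 vs 43 centers, independent centers assumed): simulated type I error 0.055, 0.055 and 0.052 at r = 0, 0.5 and 0.7. The pairing problem disappears, but change within an arm is still not tested.
- One test across the four group-by-time cells: type I error 0.046, 0.040 and 0.041 at the same r. This is only mildly conservative, but it responds to any difference among cells and does not isolate pre-post change.

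**The case against.** The strongest objection is that misuse is not shown. The SAP names Group and Time, then picks tests by distribution, and never says that Kruskal-Wallis compared baseline with post values. A reader might infer that it did and that the Aim 2 p-values are therefore wrong. The text does not support that, because between-arm use would be compatible with it. This stands, and it is why the point is put as two alternatives.

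A reader might likewise infer that unpaired t-tests were run. The phrase covering t-tests and ANOVA admits paired and repeated-measures forms, and the authors plainly knew of pairing from Aims 1, 3 and 4. That part is an ambiguity, not a demonstrated error.

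A reader might also infer a large, established loss of power. The pilot's 42% decrease in live pests (Protocol 8.6) invites it. Poisson counts with a gamma-distributed center mean (mean 4, shape 1, assumed) give 44% for Kruskal-Wallis against 97% for signed-rank. But that model holds each center's underlying rate fixed between visits, which implies a baseline correlation of 4/(4+1) = 0.80. Letting the rate vary so that the correlation is 0.32 gives 44% against 66%. No document reports the correlation.

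Finally, the consequence is bounded. The SAP calls the tobit models its primary inferential analyses, and pre-post change is the non-randomized contrast. Protocol 8.6 raises possible seasonal differences for dust; a paired test would not remove such an effect if it also touched Aim 2 outcomes. This limits the weight of the point but does not supply the missing test.

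**Conclusion.** The point holds as a gap in the specification with a conditional cost. For a non-normal Aim 2 outcome, the pre-post comparison that Hypothesis 2 asks for is either made with a test that ignores pairing or has no named test.

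In the first case the error is a conservative p-value under positive correlation. False positives are not inflated, and Kruskal-Wallis yields no interval that could be wrong. The size rests on assumed values of n, shift and correlation. The power loss runs from none at r = 0 to about 45 points (lognormal) or 50 points (normal) at r = 0.7, and is small for pooled data with a larger effect. Repeated checklists on the same premises make zero correlation unlikely, but that is a judgment and not a figure from the documents.

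The correction is worth making. It does not affect the tobit analyses of Aims 3 and 4.

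**What to change.** In SAP Specific Aim 2:
- State, for each outcome, which contrast each test addresses: pre-post within arm, or between arms.
- For pre-post, use the Wilcoxon signed-rank test on each center's post-minus-baseline difference for non-normal outcomes, and a paired t-test or repeated-measures ANOVA with center as the repeated unit for normal outcomes. Policy and pest counts can give zero differences, so say how these are handled.
- Keep Kruskal-Wallis only for comparisons between different centers, such as change scores between arms. This settles pairing only. Whether centers within a county are independent, given that Protocol 8.4 randomizes counties, is a separate question.

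The cost is a few sentences and a rerun of a few tests on data already collected. If paired tests were in fact run, only the wording changes. The downside is that centers missing one of the two visits drop out of the paired tests, so report the number of pairs for each outcome.

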Specific Aim 3: To determine if an IPM intervention reduces pesticide contamination in the intervention IPM child care centers compared to the PA control centers. (a) **Unit of Analysis:** Child care centers. (b) **Dependent Variable:** Pesticide concentrations in dust. (c) **Independent Variables: Group, Time, and Cohort.** Tobit regression models were conducted with an additional random intercept term for child care center to account for correlations within centers across timepoints (baseline, post-intervention). The concentrations and detection of the 15 pesticides measured in dust were analyzed separately using the STATA command 'tobit'.

Specific Aim 4: To determine if an IPM intervention reduces children's exposure to pesticides in the IPM intervention child care centers compared to the children in the PA control centers. (a) **Unit of Analysis:** Enrolled children with complete wristband data at baseline and post-intervention aggregated by child care center. (b) **Dependent Variable:** Pesticides measured in children's wristbands worn at the child care. (c) **Independent Variables: Group, Time, and Cohort.** Pesticide concentrations analyzed in the silicone wristbands. (c) **Independent Variables: Group, Time, and Cohort.** Tobit regression models were conducted with an

additional random intercept term for child care center to account for correlations within centers across timepoints (baseline, post-intervention). The concentrations and detection of the 13 pesticides measured in dust were analyzed separately.

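### SAP Aims 3 and 4 do not specify the Group × Time contrast their hypotheses need; Aim 3 also pairs a random-intercept model with a single-level command and gives no binary model for detection

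*SAP*

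**What the plan says.** The opening paragraph of the SAP makes tobit the main analysis: "Primary inferential analyses were performed using tobit regression models which provided an approach for modeling repeatedly measured and clustered dependent variables in this study". The package cited there is SAS.

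Under Specific Aim 3 the declared dependent variable is the dust concentration and the terms are "Independent Variables: Group, Time, and Cohort". The text continues "Tobit regression models were conducted with an additional random intercept term for child care center", with baseline and post-intervention as the two timepoints, and ends "The concentrations and detection of the 15 pesticides measured in dust were analyzed separately using the STATA command 'tobit".

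Specific Aim 4 repeats the variable list and the random intercept. Its closing sentence is "The concentrations and detection of the 13 pesticides measured in dust were analyzed separately". It names no command, and it refers to dust although the outcome is the children's wristbands.

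Hypotheses 3 and 4 (Protocol section 8.2) predict post-intervention levels that are lower than before the intervention and also lower than in the control centers.

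For neither aim does the SAP state the tested coefficient, the outcome scale, the censoring limits or a binary model for detection.

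**The concern.** With baseline and post-intervention values in one model, a hypothesis about change relative to control is tested by Group × Time. A model holding only the listed terms has no such coefficient, so a reader would take Group as the intervention effect. Group mixes the baseline difference with the post-intervention difference.

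For Aim 3 there is a second problem. Tobit deals with left-censoring and the random intercept deals with repeated measures, but the command named has no random intercept. If it was run as named, a center's two samples were treated as independent. That makes the standard error too small for Group and too large for Group × Time.

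A third problem is that detection is yes/no. Read literally, Aim 3 sends it to a model for censored normal data.

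The SAP calls these the primary inferential analyses and reports them as done. The preliminary studies section of the Protocol (8.6) reports no significant year 1 decrease in dust pesticides. A reader must be able to tell a true null from an inefficient or mis-targeted model.

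**Working it through.** The documents give no power, effect size, SD, censoring rate or within-center correlation for these aims, so there is no figure of the plan's own to reproduce.

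**1. What the listed terms estimate.** Let d be the baseline difference (IPM minus control) and δ the intervention effect. The post-intervention difference is d + δ.
- Group × Time estimates (d + δ) − d = δ.
- Group in a model without the interaction, with every center measured twice, averages the two differences: [d + (d + δ)]/2 = d + δ/2.

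With d = 0 this is half the effect. It is exact for uncensored data and approximate under censoring. Any realised baseline difference passes in full into Group and cancels out of Group × Time.

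**2. Ignoring the center.** Let ρ be the correlation between a center's two samples. Relative to independence, the variance of a center's mean is multiplied by 1 + ρ and that of its change by 1 − ρ. For a nominal two-sided 5% test (sidedness is not stated, so two-sided is assumed), in a normal approximation without censoring:
- Group: type I error = 2[1 − Φ(1.96/√(1+ρ))]
- Group × Time: type I error = 2[1 − Φ(1.96/√(1−ρ))]

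| ρ (assumed) | Group | Group × Time |
|---|---|---|
| 0.2 | 7.4% | 2.8% |
| 0.5 | 11.0% | 0.6% |
| 0.8 | 14.4% | <0.1% |

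At ρ = 0.5 the two arguments are 1.96/1.225 = 1.60 and 1.96/0.707 = 2.77.

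**3. Simulation with censoring.** Inputs: 85 centers (the SAP gives this number for survey and observational data), split 43/42 (assumed); two timepoints; total SD 1; ρ = 0.5; a detection limit that censors 30% when δ = 0; and δ of 0 or −0.5 SD. The last four are assumptions. Cohort and county were not modelled. There were 200 trials per scenario, so a rejection rate has a standard error of up to √(0.25/200) = 3.5 points.

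| Tested term and model | Rejects, δ = 0 | Mean estimate, δ = −0.5 | Rejects, δ = −0.5 |
|---|---|---|---|
| Group, no interaction, plain tobit | 10% | −0.23 | 33% |
| Group, no interaction, random intercept | 7% | −0.23 | 21% |
| Group × Time, plain tobit | 1% | −0.47 | 24.5% |
| Group × Time, random intercept | 6% | −0.47 | 53% |

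The Group estimate is half of the interaction estimate (0.23/0.47 = 0.49), as step 1 predicts. The 33% in the first row is not usable power, because that test already rejects too often under the null. With the interaction present, dropping the random intercept cuts power from 53% to 24.5%.

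**4. Detection.** Tobit fitted to a 0/1 variable returned finite estimates and standard errors in the one dataset tried. Such a model is misspecified, but software will run it.

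**The case against.** The strongest reply is that the SAP is loosely written and the analysis may be sound.

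- **The variable list is not an equation.** Aim 1 lists Group and Time but uses paired t-tests, which have no Group term, so these lists are shorthand. An interaction may have been fitted. This stands, but the SAP still does not say which coefficient answers the hypothesis, and a reader who follows the list gets the wrong one.
- **The random intercept is stated outright.** The SAP says the models had an "additional random intercept term for child care center", and the command name may be loose. That is plausible. It means the type I error figures for plain tobit are conditional on its having been run. That plain tobit is single-level is general software knowledge, not something the documents say. The clash between SAS and Stata is visible in the text itself.
- **Concentrations and detection may mean concentrations with non-detects left-censored.** Tobit handles that properly. The reading is possible, but the SAP does not say so and gives no limits.
- **The sizes rest on assumed inputs.** That is correct. They also treat centers as independently assigned, whereas the Protocol's design section (8.4) assigns matched counties, four in all.

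A reader might go further and infer that the model cannot be fitted. It can: the random-intercept tobit returned estimates in all 200 trials of each scenario, and the model without an interaction fits as well. A reader might also infer that concentrations were left untransformed. The SAP is silent on scale, and silence does not show that.

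**Conclusion.** The point holds as a specification fault that would give the wrong estimate if the plan were followed as listed. The missing Group × Time contrast applies to both aims and rests on the documents alone. The consequence, a Group coefficient of about half the effect, is algebraic; it requires only that a main-effects model was fitted to both timepoints and that arms were balanced at baseline.

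The conflict between random intercept and command, and the literal application of tobit to detection, are documented for Aim 3 only. Aim 4 names no command, so there the model for detection is simply unspecified.

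The type I errors of about 11% (Group) and 0.6% (Group × Time) apply only if plain tobit was run with no allowance for center, and only at an assumed correlation of 0.5. They and the power figures illustrate scale and do not describe this trial, since they ignore county-level assignment. The documents do not show which model was actually run.

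**What to change.** For both aims:

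- Name one package and a random-intercept tobit routine (in Stata, metobit or xttobit with the re option), left-censored at each pesticide's detection limit.
- Write out the fixed effects as Group, Time, Group × Time and Cohort, and name Group × Time as the tested intervention effect.
- State the outcome scale. If concentrations are right-skewed, use the natural log and report the effect as a ratio with a 95% CI.
- Fit detection by mixed-effects logistic regression with the same terms, or delete the words on detection. If logistic regression is to replace tobit for rarely detected pesticides, state a detection-frequency threshold fixed without reference to group results.
- Correct the reference to dust in the closing sentence of Aim 4.
- Re-run any Aim 3 or 4 result that came from plain tobit or from a model without Group × Time.
- State that the center random intercept does not account for randomisation by county, as a limit on the standard errors.

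The cost is SAP wording and analyst time on existing data. If the correct model was already fitted, only the wording changes.
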